9.5 STUDY SIZE

We assume that patients treated with Spiolto[®] Respimat[®] will have a CCQ therapeutic success rate similar to the SGRQ responder rate. In the TONADO studies^v patients treated with Spiolto[®] Respimat[®] had a 57.5% SGRQ responder rates after 24 weeks.

The TONADO was a selected trial population, so a real world population would probably show somewhat lower numbers due to the wide diversity of potential patients that will be followed up. Therefore a 50% CCQ therapeutic success rate is a reasonable assumption.

Assuming a 50% therapeutic success rate for CCQ and a sample size of 1170 patients, the 95% confidence interval for the therapeutic success rate would be between 47.1% (lower limit) and 52.9% (upper limit).

Subgroups with long acting bronchodilators at baseline (i.e., LABA only, LAMA only, LABA and ICS) will be analyzed only if they include more than 20% of all patients. In the smallest subgroup (with at least 234 patients), assuming a 50% therapeutic success rate, the 95% confidence interval would be between 43.6% and 56.4%.

To account for a 10% drop-out rate, the sample size becomes 1300 patients.

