9.7 DATA ANALYSIS

Planned analyses

More details will be described in the statistical analysis plan (SAP).

No formal hypothesis testing will be performed since this is a self-controlled study.

All patients who have received at least one dose of Spiolto[®] Respimat[®] will be included in the analysis; this is the treated set. All analyses will be performed on the treated set (as-treated analysis). If patients have missing values for an outcome, those patients will be excluded for that outcome's analysis. For example, if a patient is missing the CCQ score at Visit 1 and/ or Visit 2, that patient will be excluded from the analyses for the primary endpoint of therapeutic success and the secondary endpoint of change in CCQs from Visit 1 to Visit 2.

The assessment will be carried out using SAS[®] software. The statistical characteristics presented in the end-of-text tables will be N / mean / SD / min / median / max for continuous

variables. Tabulations of relative and absolute frequencies will be presented for categorical variables. Incidence rates and 95% CI will be given when appropriate.

The analyses will relate to the following data:

- Patient demographics (gender, age, height, weight)
- Comorbidities (main diagnosis and concurrent diagnosis according to MedDRA, version valid as at the time of database closure)
- COPD related and other concomitant medication (according to the WHO classification, version valid at the time of database closure)
- History of smoking
- Reported exacerbations
- Breathlessness based on mMRC score at visit 1
- Therapeutic success based on CCQ score; primary outcome
- Changes from Visit1 to Visit 2 in the CCQ and CCQ-4 score; secondary outcome
- Patient satisfaction with Spiolto[®] Respimat[®] at visit 2 only; secondary outcome
- General condition of the patient: evaluated by the physician (Physician's Global Evaluation (PGE)), secondary outcome
- Willingness to continue; secondary outcome
- Adverse Drug Reactions (ADR & SADR), fatal AEs, pregnancies
- GOLD spirometric classifications (1, 2, 3, 4) and GOLD patient groups (B, C, D)
- Details of treatment with inhaled respiratory agents before the study
- Details of treatment with respiratory agents during the study
- Reasons for ending treatment during the observation period
- Details of treatment continuation / discontinuation

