9.7.3 Handling of missing data

For rules regarding the imputation of CCQ score, refer to www.ccq.nl (Section health care professionals, Scoring, missing data rules). No other missing data will be imputed. Every effort will be made to collect complete data at the specified time points. Any removal from the analysis will be documented, stating the site and patient number as well as the reason for removal.

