### 2.2 Display templates for in- or end-of-text reports

#### 2.2.1 End-of-text table templates

##### 2.2.1.1 15.1 Trial subject

##### 2.2.1.1.1 15.1.1 Disposition of subjects

Table 15.1.1 1: Disposition

	N (%)
Patients recruited {patient.id}	xx (100.0)
Patients with visit 1 {anamnesis.done}	xx (yy.y)
Reason for not performing Visit 1 {anamnesis.done_reason}	
Adverse event	xx (yy.y)
Serious adverse event	xx (yy.y)
Patient's wish	xx (yy.y)
Withdrawn consent	xx (yy.y)
Lost to follow-up	xx (yy.y)
Patient died	xx (yy.y)
Other	xx (yy.y)
Study participation not possible {patient.no_participation}	xx (yy.y)
Patients with visit 1, but no registration {anamnesis.done}{registration.registered_by}	xx (yy.y)
Patients not treated	xx (yy.y)
Patients included in Treated Set	xx (yy.y)
Patients with Visit 2 {visit.done}	xx (yy.y)
Reason for not performing Visit 2 {visit.done_reason}	
Adverse event	xx (yy.y)
Serious adverse event	xx (yy.y)
Patient's wish	xx (yy.y)
Withdrawn consent	xx (yy.y)
Lost to follow-up	xx (yy.y)
Patient died	xx (yy.y)
Other	xx (yy.y)
Patients with Visit 2- Continuation of medication after end of observation (Spiolto ® Respimat ® ) {visit.spolto_continued}	xx (yy.y)
Patients with Visit 2- Discontinuation of medication after end of observation (Spiolto ® Respimat ® )	xx (yy.y)
Reason for discontinuation of Spiolto ® Respimat ® {visit.spolto_reason}	
Adverse event	xx (yy.y)
Serious adverse event	xx (yy.y)
Patient's wish	xx (yy.y)
Withdrawn consent	xx (yy.y)
Lost to follow-up	xx (yy.y)
Patient died	xx (yy.y)
Other	xx (yy.y)

Patients included in FAS	xx (yy.y)
Reason for not included in FAS	
Available total CCQ score at visit 1 only	xx (yy.y)
Available total CCQ score at visit 2 only	xx (yy.y)
No available total CCQ score at all	xx (yy.y)
Not included in TS	xx (yy.y)

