**2.3 Sensitivity analysis I- Time between Visit 1 and Visit 2**

**Sensitivity analysis- Table 1: Full Analysis Set- Time between Visit 1 and Visit 2 [weeks]**

Anamnesis.date.; visit.date	N	Mean	Std	Min	Median	Max	Nmiss
Sensitivity analysis I- Time between Visit 1 and Visit 2							

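### The primary success rate is a complete-case rate, and no planned analysis shows how far patients without a CCQ score at both visits could move it

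*Protocol*

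**What the plan says.** Protocol 9.7 defines the treated set as everyone with at least one dose and bases all analyses on it. It then narrows each outcome to the patients who have it: "If patients have missing values for an outcome, those patients will be excluded" from the analysis of that outcome. For a patient who lacks the CCQ score at either visit the text is explicit: "that patient will be excluded from the analyses for the primary endpoint of therapeutic success". Protocol 9.7.3 defers to the questionnaire's own rules for unanswered items and adds "No other missing data will be imputed".

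The SAP applies this through the FAS. Its disposition table (Table 15.1.1 1) gives the reasons for being outside the FAS, one of which is "Available total CCQ score at visit 1 only". The primary table (Table 15.2.1 1) is run on the FAS. Two sensitivity analyses are planned, both on the FAS: "Sensitivity analysis I- Time between Visit 1 and Visit 2" (SAP 2.3), and a restriction to patients whose exacerbation count was not estimated (SAP 2.4).

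Two pieces of SAP text point the other way. Section 1 divides successes by the total number of patients without naming a set. The footnote to Table 15.2.1 1 bases the percentage on all patients whether or not a CCQ score exists, and the table has a row for missing values.

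Protocol 9.5 sets the precision: "Assuming a 50% therapeutic success rate for CCQ and a sample size of 1170 patients", the 95% interval runs from 47.1% to 52.9%. It then says "To account for a 10% drop-out rate, the sample size becomes 1300 patients".

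**The concern.** The study has no comparator and plans no formal hypothesis test, so one proportion with its interval carries the primary result. Readers will take it as the success rate of patients put on the product in routine care. As planned, it is the rate among those with a scorable questionnaire at both visits, and its interval covers sampling error only.

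The loss may not be neutral. The reasons that Table 15.1.1 1 records for a missing Visit 2 include adverse event, serious adverse event and death, and these plausibly go with a poor result. Leaving such patients out would tend to raise the rate. The limitations section (Protocol 9.9) discusses selection of sites and patients, and information bias, but not attrition. Because both sensitivity analyses stay within the FAS, neither can bring back a patient without a Visit 2 score.

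**Working it through.** **Inputs.** From Protocol 9.5: success rate 50%, 1170 evaluable patients, 10% drop-out, 1300 enrolled. *Assumption:* the whole 10% consists of treated patients with a baseline CCQ but no Visit 2 CCQ, which is 1300 − 1170 = 130 patients. The protocol does not say how the 10% arises.

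**1. The plan's own figures.**
- Half-width = 1.96 × √(0.5 × 0.5 / 1170) = 2.87 points, which gives 47.1% to 52.9%. This matches Protocol 9.5.
- 1170 / 0.90 = 1300. This matches too.

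**2. Rate in all 1300.** With 0.5 × 1170 = 585 successes among complete cases and an assumed success p in the 130 missing patients, the rate is (585 + 130p) / 1300.

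| Assumed success in missing patients | Rate in all 1300 | Shift from 50.0% |
|---|---|---|
| 0% | 585/1300 = 45.0% (95% CI 42.3 to 47.7) | −5.0 points |
| 20% | 611/1300 = 47.0% | −3.0 points |
| 30% | 624/1300 = 48.0% | −2.0 points |
| 40% | 637/1300 = 49.0% | −1.0 point |
| 50% | 650/1300 = 50.0% | 0 |
| 100% | 715/1300 = 55.0% (95% CI 52.3 to 57.7) | +5.0 points |

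**3. When the shift passes the sampling half-width.** The size of the shift is 0.10 × |0.50 − p|. It exceeds 0.02865 when p is below 0.50 − 0.2865 = 21.3% or above 0.50 + 0.2865 = 78.7%.

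**4. Dependence on the drop-out rate.** With 50% success in complete cases the largest possible shift is 0.5 × the drop-out rate.
- 5% drop-out (1235 evaluable): 2.5 points, against a half-width of 2.79.
- 10% drop-out (1170 evaluable): 5.0 points, against 2.87.
- 20% drop-out (1040 evaluable): 10.0 points, against 3.04.

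**5. What the SAP shows about patients outside the FAS.**
- Table 15.1.1 1 gives counts and reasons. Listing 2 gives FAS membership and the reason for exclusion, patient by patient.
- Listings 3 to 5, on the Treated Set, give GOLD group, age, prior treatment and smoking under the same patient numbers.
- GOLD group, spirometric class and smoking are tabulated on the Treated Set and again, as subgroup totals, on the FAS, so part of the excluded patients' profile follows by subtraction.
- CCQ values appear only on the FAS (Tables 15.2.1 2 and 15.2.1 3, Listings 13 and 14). Baseline CCQ for patients outside the FAS is shown nowhere.

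**The case against.** The strongest reply is that this is a descriptive study with no success threshold, so moving from 50% to 45% changes no pre-specified conclusion. A reader could also compute the bounds from the success count and the disposition table. Both points are correct, and they lower the severity. They do not supply a pre-specified estimate with an interval, and one added after the results are known would be open to selective reporting.

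Three stronger readings are tempting, and the documents do not support them.

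- *A reader might infer that attrition bias will exceed the stated precision.* Five points requires every missing patient to fail, or every one to succeed. Less extreme assumptions give 1 to 3 points, and at 5% drop-out even the worst case is smaller than the half-width. The figure of 130 is itself an assumption. Table 15.1.1 1 also provides for patients who were never treated, who had Visit 1 but no registration, or who have a CCQ at Visit 2 only. If these are part of the 10%, fewer than 130 patients are at issue.
- *A reader might infer that the rate is biased upwards.* That is plausible but not shown. Patient's wish, withdrawn consent, loss to follow-up and other reasons say nothing definite about the CCQ. Patients who stop treatment but complete the CCQ at Visit 2 are kept, because the visit schedule (Protocol Table 9.2.3.1) collects the reason for stopping and the CCQ at the same visit. Partly completed forms still count if enough items are answered: three of four symptom items, three of four functional items and both mental items (SAP section 1).
- *A reader might infer that the excluded patients are invisible.* The disposition table and Listings 2 to 5 allow a partial comparison. The gap is narrower: no side-by-side table and no baseline CCQ outside the FAS.

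The point also depends on the unsettled denominator. If the total number of patients means the treated set, missing patients already count as not successful. The FAS exclusion reasons argue against that reading, since they leave the missing row empty and the footnote without effect, but the SAP should say so.

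**Conclusion.** The point holds as a should-fix. The primary rate leaves out treated patients without a calculable total CCQ at both visits, and no planned estimate tests what that does. Under the assumption that all 130 drop-outs are treated patients with a baseline score only, and with 50% success in complete cases, the rate in all 1300 lies between 45.0% and 55.0%. These are limits on what the missing patients could do, not an expected bias. The documents establish neither its direction nor that it would exceed sampling error.

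**What to change.** Keep the complete-case rate as the primary analysis and add the following to the SAP before results are seen:

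1. A third sensitivity analysis that repeats Table 15.2.1 1 on Treated Set patients with a baseline total CCQ, counting a missing Visit 2 total CCQ as not successful, with a 95% CI. Label it a conservative bound and give the best-case bound beside it.
2. One table of baseline CCQ, GOLD group, prior therapy and age for Treated Set patients in the FAS and not in the FAS, side by side.
3. One stated denominator, used both in the definition of the success share in section 1 and in the footnote to Table 15.2.1 1. If the sponsor means the treated set, the missing-as-not-successful rate becomes primary and the complete-case rate should be the supporting figure.

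The cost is SAP wording and two tables from data already collected. The supporting figure may be up to about 5 points less favourable than the headline at 10% drop-out.

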9.7.1 Main analysis

For the primary outcome, the proportion of patients with CCQ therapeutic success will be presented together with the 95% confidence interval.

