9.2 SETTING

9.2.1 Study sites

It is planned that data of approximately 1300 patients from approximately 400 sites in Germany will be collected. Site selection will be performed to reflect routine COPD care in Germany in order to secure representativeness of the COPD population. A log of all patients included into the study (i.e. having given informed consent) will be maintained in the ISF at the investigational site irrespective of whether they have been treated or not.

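### The planned precision and the primary 95% interval take no account of patients being nested in about 400 sites; if CCQ success is positively correlated within site, the interval is modestly too narrow.

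*Protocol*

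**What the plan says.** Protocol 9.2.1 plans data on "approximately 1300 patients from approximately 400 sites in Germany". Patients are enrolled consecutively (9.2.3, 9.4).

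Protocol 9.5 justifies the study size by precision alone. It begins "Assuming a 50% therapeutic success rate for CCQ and a sample size of 1170 patients" and concludes that the 95% interval "would be between 47.1% (lower limit) and 52.9% (upper limit"). For a subgroup of 234 patients, at the same assumed rate, "the 95% confidence interval would be between 43.6% and 56.4"%. Then: "To account for a 10% drop-out rate, the sample size becomes 1300 patients". The section contains no ICC, design effect or reference to site.

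For the analysis, Protocol 9.7.1 says only that "the proportion of patients with CCQ therapeutic success will be presented together with the 95% confidence interval". Section 9.7 leaves further detail to the SAP. SAP section 1 defines therapeutic success but gives no interval method. SAP Table 15.2.1 1 has a column for the 95% CI and nothing about how it is computed. Table 15.2.1 3 does the same for the mean change in CCQ. In the SAP, site appears only as an identifier in the listings.

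**The concern.** Patients of one practice are chosen and treated by the same prescriber, so their outcomes may resemble each other more than those of patients from different practices. Inhaler training and visit timing may also be similar within a practice. The documents do not establish this: training and visit dates are recorded per patient. But it is plausible enough that a multi-site plan should deal with it. Protocol 9.9 discusses selection bias at site level but not correlation within site.

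With positive correlation, 1170 patients carry less information than 1170 independent ones. The interval printed beside the primary result would then cover the true share less often than its 95% label says, and the precision used to justify the study size would be optimistic. The estimated share itself is not affected.

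**Working it through.** **Inputs from the documents.** Success rate p = 0.50 and evaluable n = 1170 (9.5); smallest subgroup n = 234 (9.5); about 400 sites (9.2.1).

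**Inputs assumed, because the documents give none.** ICC from 0.01 to 0.10; CV of site size 0 (equal sites) or 1 (very unequal sites).

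**Step 1: reproduce the plan's figures.** The simple binomial half-width is 1.96 × √(p(1 − p)/n).
- n = 1170: 1.96 × √(0.25/1170) = 2.87 points, giving 47.13% to 52.87%. This matches 47.1% to 52.9%.
- n = 234: 1.96 × √(0.25/234) = 6.41 points, giving 43.59% to 56.41%. This matches 43.6% to 56.4%.
- 1170/0.90 = 1300. This matches.

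Wilson intervals also match both lines (47.14% to 52.86%; 43.65% to 56.35%). Clopper-Pearson matches at 1170 but not at 234 (43.42% to 56.58%). Whichever of the matching methods was used, the design effect is 1. The figures are correct on their own inputs; the independence assumption is simply unstated.

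**Step 2: cluster size.** 1170/400 = 2.925 evaluable patients per site.

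**Step 3: design effect.** DE = 1 + (m(1 + CV²) − 1) × ICC, with m = 2.925. The multiplier of ICC is 1.925 at CV 0 and 4.85 at CV 1. The half-width becomes 2.87 × √DE. The coverage of the unadjusted interval is 2Φ(1.96/√DE) − 1.

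| ICC | CV | DE | Half-width (points) | Interval | Coverage of unadjusted interval |
|---|---|---|---|---|---|
| 0.01 | 0 | 1.02 | 2.89 | 47.1–52.9% | 94.8% |
| 0.01 | 1 | 1.05 | 2.93 | 47.1–52.9% | 94.4% |
| 0.02 | 0 | 1.04 | 2.92 | 47.1–52.9% | 94.6% |
| 0.02 | 1 | 1.10 | 3.00 | 47.0–53.0% | 93.9% |
| 0.05 | 0 | 1.10 | 3.00 | 47.0–53.0% | 93.9% |
| 0.05 | 1 | 1.24 | 3.19 | 46.8–53.2% | 92.1% |
| 0.10 | 0 | 1.19 | 3.13 | 46.9–53.1% | 92.7% |
| 0.10 | 1 | 1.49 | 3.49 | 46.5–53.5% | 89.2% |

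**Step 4: subgroups.** If a 20% subgroup is spread evenly over equal sites (an assumption), each member has about 1.925 × 0.2 = 0.385 same-site peers in that subgroup. DE is then about 1.02 at ICC 0.05 and 1.04 at ICC 0.10, and the half-width moves from 6.4 to at most 6.5 points.

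**The case against.** The strongest reply is that the effect is small and changes no decision. Many sites with about three patients each is already a design that limits clustering. With equal sites, an ICC of 0.02 leaves the interval as printed and an ICC of 0.05 moves each limit by 0.1 point. Protocol 9.7 plans no formal hypothesis testing, and the primary outcome has no threshold or margin that a shift of a few tenths of a point could cross. All of this stands, and it makes the point minor. It does not remove it: the interval is labelled 95%, precision is the only basis given for the study size, and the adjustment uses data already held.

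A reader might also infer several stronger things that the documents do not support:

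- **That the interval is certainly too narrow.** This needs a positive ICC, and none is given.
- **That the sentence in 9.7.1 itself shows independence.** It names no method. The evidence is that the 9.5 figures reproduce only at design effect 1, and that the SAP is silent on site.
- **That the primary interval is the study's only inferential statement.** The SAP also plans intervals for CCQ means and changes, and chi-square, Fisher, Wilcoxon and Kruskal-Wallis p-values in its subgroup tables.
- **That the physician's PGE rating makes the primary result clustered.** The primary outcome is the CCQ, which the patient completes, so a shared PGE rater says nothing about it.
- **That all subgroup intervals and p-values under-cover.** Step 4 of the working shows a smaller effect on subgroup intervals. For contrasts between patients of the same site, such as age or smoking, ignoring positive correlation can make the comparison conservative.

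**Conclusion.** The point holds as a minor, conditional one. The planned precision assumes independent patients, and no document plans an interval that respects site. If success on the CCQ is positively correlated within site, the nominal 95% interval is modestly too narrow. Under the assumed ICC of 0.02 to 0.10 and CV of 0 to 1, the half-width is about 2.9 to 3.5 points instead of 2.87, and coverage is about 94.6% to 89.2%. The 89.2% figure requires the largest ICC and very unequal sites together.

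It would be wrong to read this as a sample-size error. The figures in 9.5 follow from their stated inputs, and the study has no power or margin to lose.

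**What to change.** - **Protocol 9.7.1 and the SAP (section 1, Tables 15.2.1 1 and 15.2.1 3):** name the interval method, and compute the 95% intervals for the success share and the mean CCQ change with site as the cluster. A survey procedure with a CLUSTER statement does this, as does GEE with robust variance. With an independence working correlation, GEE also leaves the point estimate equal to the plain patient-level share.
- **Reporting:** give the observed ICC for therapeutic success and the distribution of evaluable patients per site, so that readers can see how much the adjustment mattered.
- **Protocol 9.5:** add a sentence that 47.1% to 52.9% assumes independent patients, with the design-effect range (about 1.04 to 1.49 for ICC 0.02 to 0.10 and CV 0 to 1).

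The cost is SAP wording and one procedure option in SAS, which the protocol already specifies. Site is already captured. The downside is a slightly wider interval; if the ICC is near zero, almost nothing changes.

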9.7.3 Handling of missing data

For rules regarding the imputation of CCQ score, refer to www.ccq.nl (Section health care professionals, Scoring, missing data rules). No other missing data will be imputed. Every effort will be made to collect complete data at the specified time points. Any removal from the analysis will be documented, stating the site and patient number as well as the reason for removal.

9.8 QUALITY CONTROL

To improve and secure data quality, automatic data checks upon data entry will be done within the eCRF. In the eCRF, plausible ranges of values for numeric data entries as well as logical data entries and listings will be provided for each entry field. Based on this, checks on completeness and plausibility will be performed upon data entry in the eCRF.

Validity of data entry thus is ensured by integrated validation checks performed by the system, indicating missing or implausible entries to the document list or investigator. All corrections will be visible from the systems audit trail.

Source data verification is planned to be performed in about 10% of the planned sites in this study. However, in case of decreasing compliance (i.e. of missing data, data discrepancies, protocol violations, etc.) a for-cause audit or risk-based monitoring visit will be performed.

